5.1 Inclusion criteria (all must be met)

- 1)Subjects ≥ 18 years old, regardless of gender;The diagnosis was immune thrombocytopenia.
- 2)Platelet $\leq 75 \times 10^9/L$ prior to scheduled elective surgery⁹, Surgery Major or minor surgery is defined by the treating surgeon and hematologist based on the duration

and complexity of the procedure and the risk of bleeding for the patient;
3)Willing to participate in clinical study and sign informed consent form.

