1.2.5.1 A Phase III Clinical Study of Hytrombopag in Primary Immune Thrombocytopenia

In a multicenter, randomized phase III clinical study of hetrombopag in primary immune thrombocytopenia, 424 patients ($PLT < 30 \times 10^9 / L$ at 48 hours prior to enrollment) with at least 6 months of history of primary ITP who had failed or relapsed to at least one line of ITP therapy⁹ After 10 weeks of treatment, the patients entered the 14-week open-label phase. The treatment group continued to receive the dose adjusted in the previous phase, while the placebo group received the positive control drug eltrombopag (initial dose 25 mg/d) and maintained $PLT(50-150) \times 10^9 / L$. The results showed that after 8 weeks of treatment, hetrombopag achieved therapeutic response ($PLT \geq 50 \times 10^9 / L$) was significantly higher than placebo (Hytrombopag 2.5 mg vs. Hytrombopag 5 mg vs. placebo: 58.9% vs. 64.3% vs. 5.9%, $P < 0.0001$), and the onset of action was rapid, with a median of 21 days for the 2.5 mg group, respectively (95CI: 15-25), 5mg group 14 days (95%CI: 8-14). 24 weeks of treatment with hitrombopag produced a sustained platelet response, with 44.8% of subjects having platelet counts $\geq 50 \times 10^9 / L$ times greater than 75% of total detection times, platelet count $\geq 50 \times 10^9 / L$ The median (minimum, maximum) maximum duration of/L was 64(6,168) days and the median total duration

was 103(6,168) days.

1.2.5.2 A Phase II Clinical Study of Hytrombopag in Severe Aplastic Anemia with Poor Response to IST

In a multicenter, single-arm, open-label phase II study of severe aplastic anemia with poor response to IST, 55 SAA patients who had a poor response to IST and were not transplant candidates/unwilling received hetrombopag at a starting dose of 7.5 mg.⁹ The results showed that 23 patients (41.8%) achieved hematological response at week 18 and 24 patients (43.6%) achieved hematological response at week 24. For those patients who achieved hematologic response during the study, the median remission time was not reached due to the small number of relapses, and the relapse-free survival rates at 9 and 12 months were 82.2%(95% CI: 62.2%, 92.2%).

2 Purpose of the study

To observe the efficacy and safety of hytrombopag ethanolamine tablets in the treatment of thrombocytopenia in patients undergoing elective surgery.

3 Study endpoints

3.1 primary study endpoint

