Proportion of patients achieving perioperative platelet count goals ($\geq 80 \times 10^9 \mu \text{g/L}$ for major surgery and $\geq 50 \times 10^9 \mu \text{g/L}$ for minor surgery) without rescue therapy

3.2 secondary study endpoints

- 1)Median time to platelet count target;
- 2)Subject platelet count $\geq 50 \times 10^9 \text{L}$ maximum duration;

- 3)Subject platelet count $\geq 80 \times 10^9/L$ maximum duration;
- 4)Proportion of patients with surgical delay due to thrombocytopenia;
- 5)Proportion of patients undergoing surgery on schedule;
- 6)Incidence and severity of bleeding in patients;
- 7)Proportion of patients receiving emergency treatment;
- 8)Safety: Adverse events (AEs): include type, incidence, severity, duration, and relationship to study drug.

4 Experimental design

This is an investigator-initiated, single-arm, prospective clinical study to evaluate the efficacy and safety of hytrombopag in the treatment of thrombocytopenia occurring prior to scheduled surgery.⁹After signing the informed consent form, the patients will enter the screening period (up to 7 days) and receive oral treatment with hytrombopag after screening. The specific dosage regimen is: 7.5 mg, once daily, orally before bed on an empty stomach, lasting for up to 14 days, $PLT \geq 100 \times 10^9/L$. During oral administration of hytrombopag, when $PLT \geq 200 \times 10^9/L$, the administration was suspended and the hemogram was monitored every 7 days until $PLT < 100 \times 10^9/L$. During the treatment period, blood routine was monitored once every 3 days, $PLT \leq 30 \times 10^9/L$ or $\geq 300 \times 10^9/L$. Patients will have an end-of-treatment visit within 7 days of treatment discontinuation, followed by a 30-day safety follow-up period.

5 Management of Subjects

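### Minor-surgery patients entering at 50-75 x10^9/L are already at the count goal, so the primary proportion mixes patients at goal on entry with patients raised to goal and should also be reported by baseline goal status

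*Protocol*

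**What the plan says.** All counts below are x10^9/L.

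- **Entry.** Inclusion criterion 2 (Protocol 5.1, and the same in the protocol summary) has one ceiling for both surgery types: "Platelet $\leq 75 \times 10^9/L$ prior to scheduled elective surgery". The same criterion says how the surgery type is set: "Major or minor surgery is defined by the treating surgeon and hematologist based on the duration" and complexity of the procedure and the bleeding risk.
- **Primary endpoint.** Section 3.1 counts a patient as a success on reaching a perioperative goal of at least 80 for major surgery, or "\geq 50 \times 10^9 \mu \text{g/L}$ for minor surgery) without rescue therapy". It asks for no rise from baseline.
- **Purpose.** Section 2 states it as "To observe the efficacy and safety of hytrombopag ethanolamine tablets in the treatment of thrombocytopenia in patients undergoing elective surgery".
- **Secondary endpoints.** Section 3.2 includes "Median time to platelet count target", "Subject platelet count $\geq 50 \times 10^9 \text{L}$ maximum duration" and "Subject platelet count $\geq 80 \times 10^9/L$ maximum duration".
- **Analysis.** Section 4 describes a single-arm study. Section 10.3.2 bases the primary analysis on the FAS, uses baseline platelet count as a covariate, and defines baseline as the last count before dosing. Section 10.4 calls the design exploratory and plans about 50 patients, with an assumed 65% meeting the goal. No hypothesis or success threshold appears under 10.2.

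**The concern.** The entry ceiling is the same for everyone, but the success threshold depends on surgery type. For minor surgery the two ranges overlap. A patient in the overlap has not met the whole endpoint on entry, since the count must hold perioperatively and no rescue may be used. That patient nevertheless needs no platelet rise to succeed.

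The stated purpose is efficacy in treating thrombocytopenia. With one arm there is no control rate to show how many of these patients would have been at goal anyway. A reader of the single FAS proportion cannot tell successes that required a rise from those that did not. The baseline covariate does not help, because it does not change who counts as a success.

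Two secondary endpoints share the problem. Duration at 50 or above can start at entry for any patient enrolled at 50-75, whatever the surgery. Time to goal is affected for minor-surgery patients if it is counted from first dose. Duration at 80 or above is not affected by the entry count, because 80 lies above the entry ceiling.

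**Working it through.** **1. The overlap, from the protocol's thresholds**

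| Surgery type | Entry count (5.1) | Goal (3.1) | At goal on entry |
|---|---|---|---|
| Major | 75 or below | 80 or above | never (75 < 80) |
| Minor | 75 or below | 50 or above | yes, if 50-75 |

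The exclusion criteria (5.2), the analysis sets (10.3.1), the primary analysis (10.3.2) and the missing-data rule (10.3.5) do not separate the patients in the last row.

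**2. The plan's own precision figure**

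The 95% Clopper-Pearson limits are the beta quantiles B(0.025; x, n-x+1) and B(0.975; x+1, n-x). With n = 50 and x = 0.65 x 50 = 32.5 they are 50.2% and 77.9%, width 27.7 points, as stated in 10.4. The half-width is 27.7/2 = 13.9 points. The sample-size arithmetic is correct, and the overlap does not affect it.

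**3. What the overlap could do to the proportion (assumption range)**

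The documents give neither the surgery mix nor the baseline distribution. Let q be the share of all patients who are minor surgery at 50-75, s their success rate, and r the success rate of everyone else. Then

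p = q·s + (1-q)·r, so r = (p - q·s)/(1-q) and p - r = q·(s - p)/(1-q).

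Take p = 65%, only because it is the plan's figure. Assumed values of q are 3% (30% minor x 10% of them at 50-75), 15% (50% x 30%) and 35% (70% x 50%), that is 1.5, 7.5 or 17.5 of 50 patients. At q = 0 the difference is zero.

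Worked cell: q = 15%, s = 90% gives r = (0.65 - 0.135)/0.85 = 60.6%, a difference of +4.4 points.

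| s | q = 3%: r (p - r) | q = 15%: r (p - r) | q = 35%: r (p - r) |
|---|---|---|---|
| 100% | 63.9% (+1.1) | 58.8% (+6.2) | 46.2% (+18.8) |
| 90% | 64.2% (+0.8) | 60.6% (+4.4) | 51.5% (+13.5) |
| 80% | 64.5% (+0.5) | 62.4% (+2.6) | 56.9% (+8.1) |
| 70% | 64.8% (+0.2) | 64.1% (+0.9) | 62.3% (+2.7) |
| 65% | 65.0% (0) | 65.0% (0) | 65.0% (0) |
| 60% | 65.2% (-0.2) | 65.9% (-0.9) | 67.7% (-2.7) |

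The sign follows s - p. Only one of the 18 cells (q = 35%, s = 100%) exceeds the planned half-width of 13.9 points.

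**4. Precision of the below-goal estimate**

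The number below goal is 50(1-q) = 48.5, 42.5 or 32.5, rounded up to 49, 43 or 33. The Clopper-Pearson limits at 65% are:

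- n = 49: 50.1%-78.1%, width 28.0 points
- n = 43: 49.0%-78.9%, width 29.9 points
- n = 33: 46.5%-80.7%, width 34.2 points

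**The case against.** **The endpoint is what section 3.1 says it is.** The FAS proportion estimates goal attainment among enrolled patients, and it does so validly. This stands, and it is why the FAS result should remain primary. A reader might infer that patients at goal on entry must be removed from the primary population. The documents do not require that, and doing so would exchange precision and the full treated population for a different question.

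**The effect may be small or absent.** This also stands. Section 1.1 describes treatment given where the procedure's count requirement makes it necessary, and exclusion 9 lets the investigator decline unsuitable patients, so few such patients may enrol. A reader might infer that the reported proportion is inflated. That holds only if these patients succeed more often than the rest, which is plausible but not established.

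**The phase III trial is not a yardstick.** It is tempting to argue that the result will be set beside the 58.9% and 64.3% in section 1.2.5.1, where "424 patients ($PLT < 30 \times 10^9 / L$ at 48 hours prior to enrollment" meant that every responder had to rise. The protocol plans no such comparison. That trial used 2.5 or 5 mg and an 8-week response in previously treated patients, and it had no goal of 80. The contrast shows that entry and response thresholds can be kept apart, but no more.

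**The surgery label.** A reader might infer that the major/minor category could be set after platelet counts are seen. The definition sits inside an inclusion criterion, and dosing follows screening (section 4), so the natural reading is that it is set before the first dose.

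**The SAP may deal with it.** Subgroup reporting and the time origin for time to goal are commonly left there, and their absence is no fault. The overlap itself comes from the eligibility criterion and the endpoint, both of which this protocol fixes.

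**A split does not isolate drug effect.** Correct. A rise from 49 to 50 still counts, and regression to the mean remains without a control. The split removes only successes that needed no rise.

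**Conclusion.** The overlap is certain from the protocol's own thresholds: a minor-surgery patient entering at 50-75 can be a primary success without any platelet rise, and the protocol does not distinguish such successes. The FAS proportion is a sound description of goal attainment but not, on its own, evidence that the drug raised platelets to goal.

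How far it differs from the rate in patients who needed a rise cannot be derived from the documents. Over the assumed range it runs from -2.7 to +18.8 points, with zero possible, and in nearly all cells it is smaller than the planned half-width. These figures rest on assumed q and s and on the planned 65%.

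The study is exploratory and states no success threshold, so no formal decision is at risk. The matter concerns interpretation, and a prespecified split answers it at little cost.

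**What to change.** Keep the FAS proportion as the primary result. Add to 10.3.2 wording such as:

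> The primary proportion is also reported, with two-sided 95% Clopper-Pearson intervals, separately for FAS patients whose last platelet count before dosing is below the goal for their surgery type (below 80 x10^9/L major, below 50 x10^9/L minor) and for FAS patients already at goal. Statements about raising platelets to target rest on the below-goal group. The surgery type assigned at eligibility is used.

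For the secondary endpoints, summarise time to goal in patients below goal at baseline, and duration at 50 or above in patients with a baseline below 50. Duration at 80 or above needs no change.

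Cost: one reporting rule using counts already collected. Enrolment and the primary population do not change. The downside is precision in the below-goal group, whose interval is wider than the 27.7 points stated for n = 50: about 30 points at n = 43 (assumed 15% overlap) and 34.2 at n = 33 (assumed 35%). The at-goal group may be too small for more than description.

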5.2 Exclusion criteria (one of which is excluded)

- 1) History of allergy to TPO-RA drugs;
- 2) Severe bleeding symptoms, such as upper gastrointestinal bleeding, bleeding of important organs, intracranial hemorrhage, etc.;
- 3) thrombotic diseases such as pulmonary embolism, arterial thrombosis and disseminated intravascular coagulation (DIC);
- 4) Anti-human immunodeficiency virus antibody or anti-Treponema pallidum specific antibody positive;
- 5) Congestive heart failure New York Heart Association (NYHA) class 3 or 4;
- 6) History of angina pectoris, myocardial infarction or cerebral infarction within 6 months prior to screening;
- 7) Active infections that are difficult to control;
- 8) Pregnant or lactating women;
- 9) Other circumstances deemed unsuitable for inclusion in the study by the investigator.

6 Dosing Regimen

Subjects must take the drug on an empty stomach every morning (overnight fasting for at least 8 hours), breakfast must not be eaten for 2 hours after dosing, and subjects are required to take all trial drugs of the day once a day, swallow the trial drugs whole, and do not chew, divide or crush them.

7. Concomitant Medications/Concomitant Therapy

The investigator has the right to decide at any time whether to give the following supportive treatment to the subject: transfusion supportive treatment (such as red blood cells and platelets). During this trial, except for the basic treatment and drugs used for

treatment or prevention of adverse events that have been taken stably before the trial, any other drugs are prohibited in principle. Any drugs used during the trial other than the trial drugs should be recorded in detail in the eCRF, and the records should include: drug name, dose, date of administration and indication for use.

8 Test observation methods

During the treatment period, blood routine was monitored once every 7 days, $PLT \leq 50 \times 10^9/L$ or $\geq 300 \times 10^9/L$. Patients will have an end-of-treatment visit within 7 days of treatment discontinuation, followed by a 30-day safety follow-up period.

9 Adverse events and evaluations

9.1 adverse event definitions

Adverse Event (AE) refers to any adverse medical event occurring in this trial from the time the subject signs the informed consent form until 28 days after the last dose, regardless of whether it is causally related to the trial drug. All adverse events should be followed up by the investigator until the event has been resolved, or recovered to baseline level, or the investigator judges that the event has turned to "stable" without further follow-up, or the subject is lost to follow-up, or the subject dies.

Adverse events include the following:

- 1)Worsening of pre-existing (before entering clinical trial) medical condition/disease (including symptoms, signs, laboratory abnormalities);
- 2)Any new adverse event: any new adverse medical condition (including symptoms, signs, newly diagnosed diseases);
- 3)Abnormal clinically significant laboratory values or results indicating a new disease or organ toxicity worse than baseline.
- 4)Decreases in platelet values were not recorded as AEs unless they were accompanied by new bleeding symptoms or worsening of existing bleeding symptoms from baseline,

or required urgent treatment.

The investigator should record any adverse event occurred by the subject in detail, including: description of adverse event and all related symptoms, onset time, severity, cause of adverse event, correlation with investigational drug, duration, measures taken, final results and outcome.

9.2 Obtaining adverse event information

Investigators should report all adverse events directly observed or spontaneously reported by subjects in concise language. In addition, subjects should be asked regularly about adverse events after the start of the trial.

9.3 adverse event record

During the trial, the adverse event record form should be truthfully filled in, including the occurrence time, severity, duration, measures taken and outcome of adverse events. Adverse events should be recorded in the adverse event form of the designated case report form.

9.4 Criteria for severity of adverse reactions

When completing the Adverse Event Form in the eCRF, the investigator will describe the severity of the adverse event using mild, moderate, and severe. For uniform criteria, the severity of the event will be graded as follows:

- **Grade 1 (mild):** usually transient, generally does not interfere with activities of daily living, does not require medication or may require minimal treatment;
- **Grade 2 (moderate):** Subject feels unwell, activities of daily living are affected, treatment is usually required to alleviate, but there is no risk of major or permanent harm to the subject;
- **Grade 3 (severe):** The activities of daily living of the subject are interrupted, or the clinical condition is seriously affected, and intensive treatment and intervention are

required;

Severe is used only to describe degree. For example, headache may appear severe in degree but cannot be classified as a serious adverse event (SAE) unless it meets the criteria for an SAE.

9.5 Criteria for determining the relationship between adverse events and investigational drug

Adverse events include all unexpected clinical manifestations. As long as these events occur after signing the informed consent form, regardless of whether they are related to the investigational drug, they should be reported as adverse events. Any discomfort complained by patients or abnormal changes in objective laboratory test indicators during treatment should be recorded truthfully, and the severity, duration, treatment measures and outcome of adverse events should be indicated. Clinicians should also comprehensively judge the relationship between adverse events and the investigational drug. The possible association between adverse events and the investigational drug was evaluated according to the five-level classification method of "definitely related, possibly related, possibly unrelated, definitely unrelated and undeterminable." "definitely related," "possibly related" and "undeterminable" were all listed as adverse drug reactions. The total of these three factors was taken as numerator when calculating the incidence rate of adverse events, and the number of all subjects used for safety evaluation was taken as denominator. The judgment criteria were as follows:

grading	judgment standard
definitely related	The type of adverse event has been identified as a known reaction type to the drug and cannot be explained by other reasons (e.g. concomitant medications and concomitant diseases). The timing of the event strongly suggests a causal relationship (e.g. withdrawal and re-administration of the drug).
possibly related	The occurrence of adverse events was in a reasonable time sequence with the administration of the investigational drug. The occurrence of adverse events may be caused by the investigational drug. It cannot be ruled out whether other factors may be caused, such as concomitant drugs or concomitant diseases. The drug was not

	withdrawn or unclear.
unlikely related	There was no evidence of a causal relationship between the occurrence of the event and the trial drug. The occurrence of the adverse event was more likely related to other factors, such as concomitant medications or concomitant diseases. However, an association between the two could not be ruled out.
not related	Adverse events are not related to the use of the investigational drug.
Unable to assess	There is insufficient information to determine the causal relationship between the event and trial medication. The investigator may change her/his causality assessment based on subsequent follow-up information and modify the AE/SAE report accordingly.

9.6 the definition of serious adverse event

Serious adverse events refer to medical events that require hospitalization or prolongation of hospitalization, disability affecting work ability, life-threatening or death, congenital malformation, etc. during the clinical trial, including the following unexpected medical events:

- Death;
- Life-threatening (defined as the subject being at immediate risk of death at the time of the event);
- Requires hospitalization or prolongation of hospitalization;
- Persistent or significant disability/loss of function;
- Congenital anomalies or birth defects;
- Other important medical events (defined as events that harm the patient or require intervention to prevent any of the above).

Hospitalization does not include the following:

- rehabilitation institutions
- sanatorium
- Regular emergency room admissions
- same-day surgery (eg outpatient/same-day/ambulatory surgery)

Hospitalization or prolongation of hospitalization not associated with worsening of an AE is not an SAE per se. Example:

- Admissions due to pre-existing diseases, no new adverse events, and no exacerbation of pre-existing diseases (e.g., to check for laboratory abnormalities that persist from pre-trial to present);
- Manage the cause of hospitalization (e.g. annual routine check-up);
- protocol-specified hospitalizations during the clinical trial (e.g., performed as per protocol requirements);
- Elective hospitalizations unrelated to worsening of adverse events (e.g. elective surgery);
- Scheduled treatments or surgical procedures should be documented throughout the trial protocol and/or in the subject's individual baseline profile;
- Admitted to hospital solely for blood product use.

9.7 reporting of serious adverse events

Any serious adverse event occurring during the clinical study and after drug discontinuation must be immediately reported to the monitor of the sponsor, the principal investigator of the clinical study site and the ethics committee of the clinical study site. Meanwhile, the investigator must fill in the serious adverse event report form (SAE), describe in detail the time of occurrence, severity, relationship with the investigational drug and measures taken, and sign the report.

Follow-up reports should be submitted immediately if the intensity of an ongoing SAE or its relationship to the study drug changes. If the investigator believes that the information previously reported for an SAE is false, a correction, withdrawal, or downgrade can be made in the follow-up report and reported according to SAE reporting procedures.

9.8 contraceptive

All subjects who are considered by the investigator to be sexually active and capable of conceiving or impregnating a partner must agree to use an effective method of contraception throughout the duration of the study (from 2 weeks prior to the first

dose of trial product to at least 30 days after the last dose).

9.9 pregnancy report

If a female subject becomes pregnant during the clinical trial, the subject withdraws from the trial, and if a male subject's partner becomes pregnant, the subject may continue the clinical trial. Pregnancy itself is not considered an SAE, but any negative pregnancy outcome (e.g. stillbirth, spontaneous abortion, fetal malformation) is considered an SAE and needs to be reported according to the time limit of SAE. If the subject also experiences an SAE during pregnancy, the SAE Report Form should be completed and reported according to the SAE Reporting Procedure.

10 Statistical analysis

10.1 statistical analysis plan

Statistical analysis will be performed using SAS statistical analysis software. Detailed statistical analysis details will be provided in the formal statistical analysis plan (SAP).

10.2 statistical hypothesis

10.3 statistical methods

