10.3.1 Statistical Analysis Data Sets

- 1)Safety analysis set (SAS): including subjects who have used the investigational drug at least once;
- 2)FAS (full analysis set): including all subjects who were randomized into the study group, who used the investigational drug at least once, and who had efficacy indicators after randomization at least once;
- 3)PPS (per-protocol set): subset of FAS, excluding subjects with serious protocol violations;

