10.3.3 Secondary Efficacy Analyses

10.3.4 Safety analysis

Adverse events occurring during the trial will be coded using MedDRA dictionary based on safety analysis set. Frequency and incidence of adverse events will be described according to system organ class (SOC) and preferred term (PT). Correlation and seriousness of adverse events will be further tabulated. Other safety indicators will be summarized by descriptive statistics. Adverse events, adverse reactions, adverse events leading to withdrawal from the trial, adverse events leading to death, Incidence rate of serious adverse events; incidence rate calculated by subsystem and symptoms/signs (count of cases: number of subjects who have experienced at least one adverse event); severity of adverse events and adverse reactions: the same adverse event occurs multiple times in the same subject, and the most serious adverse event is included in the analysis; different adverse events occur in the same subject, and the most serious adverse event is included in the analysis.

Laboratory test parameters: Descriptive summaries of laboratory test values focused on outliers.

Vital signs: Mean, maximum, minimum, median, standard deviation are used to describe the measured values and changes at each visit.

Physical examination, 12-lead ECG, etc. were analyzed descriptively.

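### Section 9.5 gives the adverse-event incidence the numerator of the adverse-drug-reaction rate, against Section 10.3.4

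*Protocol*

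**What the plan says.** Section 9.5 sets out five causality classes. Three of them (definitely related, possibly related, undeterminable) "were all listed as adverse drug reactions". The next sentence fixes a calculation: "The total of these three factors was taken as numerator when calculating the incidence rate of adverse events". For the denominator, the same sentence takes everyone evaluated for safety.

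Section 10.3.4 plans the safety analysis on the safety analysis set, defined in Section 10.3.1 as "including subjects who have used the investigational drug at least once". It describes adverse-event frequency and incidence by system organ class and preferred term, without restricting by causality. Relationship to drug comes as an additional step: "Correlation and seriousness of adverse events will be further tabulated". The list of rates to be reported opens with "Adverse events, adverse reactions, adverse events leading to withdrawal from the trial", so events and reactions are two items. The counting unit is given as "count of cases: number of subjects who have experienced at least one adverse event".

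Section 9.1 and the opening of Section 9.5 both define an adverse event irrespective of its relation to the drug. Item 8 of Section 3.2 names incidence and relationship to study drug as separate attributes of the safety endpoint.

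**The concern.** The protocol contains two rules for one rate. Section 9.5 limits the numerator of the adverse-event incidence to three causality classes; Section 10.3.4 does not limit it. Anyone writing the analysis programs or the SAP from this protocol would have to choose between them.

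The choice affects a named secondary endpoint. Under the literal Section 9.5 rule, the reported adverse-event incidence would really be an adverse-reaction incidence and would depend on investigators' causality judgements. The trial is single-arm, so there is no control rate to set beside it. Subjects are scheduled for surgery, and Section 9.1 collects events until 28 days after the last dose. It is therefore plausible, though the protocol gives no figure, that some subjects will have only events attributed to other causes. Those subjects would drop out of the adverse-event rate.

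**Working it through.** The protocol states no adverse-event rate, so there is no planned figure to reproduce. The check compares the passages and then sizes the gap.

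**Step 1: the two rules side by side**

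| Element | Section 9.5 | Section 10.3.4 |
|---|---|---|
| Rate named | Incidence of adverse events | Incidence of adverse events |
| Causality filter | Definitely related, possibly related, undeterminable only | None |
| Adverse reactions | Same three classes, so the same numerator | Separate item |
| Counting unit | A total; subjects or events not stated | Subjects with at least one event |
| Denominator | All subjects used for safety evaluation | Safety analysis set (dosed at least once) |

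The denominators are compatible. The causality filter is the contradiction. The unit in Section 9.5 is also left open.

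**Step 2: size of the gap, counted per subject**

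Inputs:
- n = about 50 subjects (Section 10.4), assuming all are dosed and so belong to the safety analysis set.
- A = subjects with at least one adverse event of any causality.
- k = subjects among A whose events are all judged unlikely or not related. The protocol gives no value, so k is an assumption.

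Formulas:
- Section 10.3.4 rate = A/n
- Literal Section 9.5 rate = (A − k)/n
- Gap = A/n − (A − k)/n = k/n

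The gap does not depend on A, and it cannot be negative because k ≥ 0.

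| k (assumed) | n | Gap |
|---|---|---|
| 0 | 50 | 0 points |
| 1 | 50 | 1/50 = 2.0 points |
| 5 | 50 | 5/50 = 10.0 points |
| 1 | 45 | 1/45 = 2.2 points |
| 1 | 55 | 1/55 = 1.8 points |

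**Step 3: illustration with an assumed event rate**

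Suppose 20 of 50 subjects (40%) have any adverse event. If 25%, 50% or 75% of those 20 have at least one event in the three classes, the literal Section 9.5 rate is 5/50 = 10%, 10/50 = 20% or 15/50 = 30%, against 40% under Section 10.3.4. Here k is 15, 10 or 5, and the gaps of 30, 20 and 10 points equal k/50. All these rates are assumed.

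**Step 4: if Section 9.5 means events**

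One subject with three related events would add 3/50 = 6.0 points under an event count, against 1/50 = 2.0 points under a subject count. The Section 9.5 figure could then exceed the Section 10.3.4 rate. The downward direction in Step 2 therefore holds only for subject counting.

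**The case against.** The strongest reply is that this is one misused term and not a chosen analysis. The sentence comes straight after the definition of adverse drug reactions and refers back to the same three classes; reading it as the adverse-drug-reaction rate removes the conflict. The protocol mixes the two terms elsewhere too: the heading of Section 9.4 speaks of adverse reactions while its text grades adverse events. Section 9.5 concerns causality criteria. The safety analysis belongs to Section 10.3.4, which already provides both rates, and Section 10.1 leaves detail to a SAP. All events are recorded whatever their causality, so either rate can be computed later. The trial is exploratory, and no stated safety threshold depends on this rate. The gap rests on assumed values of k, including zero.

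Most of this stands. A slip is the likeliest explanation, the harm is reversible, and the assumed k values do not show that any bias will occur. It is also right that the direction is fixed only for subject counts. It does not remove the contradiction: the sentence is a stated calculation rule, not a missing detail that a SAP could simply supply, and the protocol does not say which section governs.

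**Conclusion.** The concern holds. As written, Section 9.5 assigns the adverse-drug-reaction numerator to the adverse-event incidence, contrary to Section 10.3.4 and out of line with the causality-free definition of an adverse event in Section 9.1. That definition describes the event and not a rate, so the direct conflict is with Section 10.3.4.

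The consequence is modest. Counted per subject, the literal rule gives a rate equal to or lower than that of Section 10.3.4, by 2.0 points for each affected subject at n = 50 (1.8 to 2.2 points for 55 to 45 dosed subjects). The number of affected subjects is unknown. Data collection, the primary endpoint and the sample size are untouched. The point merits correction because it concerns a named secondary endpoint and the remedy is almost free.

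**What to change.** In Section 9.5, make the sentence refer to the incidence of adverse *drug reactions*: the number of subjects with at least one event judged definitely related, possibly related or undeterminable, divided by the number of subjects in the safety analysis set. Then add one sentence: *Adverse-event incidence is calculated as in Section 10.3.4, as subjects with at least one adverse event of any causality divided by the safety analysis set.*

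This removes the causality conflict and settles the counting unit. It costs one reworded sentence and one new one. It needs no extra visits, data or subjects and leaves the analysis in Section 10.3.4 as it is. The only visible effect is that the reported adverse-event rate may be higher than under a literal, per-subject reading of Section 9.5.
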